**Figure 1. Conceptual Model for Breastfeeding and Smoking Abstinence\***

\* Other hormonal mechanisms, such as progesterone, estrogen, ACTH, cortisol, and tetraiodothyronine (T4), will be included in the larger R01 grant.

must be at 28 weeks of pregnancy or earlier to ensure adequate time for prenatal breastfeeding intervention. Exclusion criteria are teen pregnancy (<18 y); current use of other tobacco or nicotine products; medical conditions contraindicating breastfeeding such as HIV infection, active tuberculosis, and breast removal; current heavy drinking (more than 2 drinks a day); current use of other psychoactive substances; being strongly against breastfeeding; and non-English speakers. To increase the possibility to obtain a representative sample of the generable population, the study will be advertised as a program to promote healthy infant feeding among pregnant women without requiring breastfeeding intention or mentioning smoking relapse prevention. We will not exclude women without current intention to breastfeed (28.6% in our pilot survey), unless they are strongly against breastfeeding (4.8%). Similarly, we will not exclude women who plan to relapse after delivery (0% in our pilot survey), as our breastfeeding promotion may motivate them to maintain abstinent for a longer period especially if they know tobacco metabolites are concentrated in breast milk.

**3.1.4 Pre-test visit.** During this visit, we will measure the participant's urine cotinine, height, and body weight. Participants will complete a survey on smoking temptations, nicotine dependence before quitting, smoking cessation history, self-efficacy to maintain smoking abstinence, smoking environment including partner smoking behaviors, breast health, breastfeeding knowledge, breastfeeding history, relationship with partner and other family members, social network, stress, negative affect, physical activity, sleep, and diet.

**3.1.5 Randomization.** At 28 weeks of pregnancy, eligible participants will be randomized into either the intervention group (N=30) or the control group (N=30) using a sequence of random numbers in blocks of 2, which can ensure equal or close numbers of participants between the two groups throughout the project.

**3.1.6 Intervention. a) Intervention group.** The goal of our breastfeeding intervention is consistent with AAP and ACOG guidelines: exclusive breastfeeding for the first 6 months of life, with continued breastfeeding as complementary foods are introduced through the infant's first year of life, or longer as mutually desired by the mother and her infant. Participant will complete 13 one-hour intervention visits: 5 during pregnancy and 8 in postpartum. Prenatal breastfeeding education will be weekly for 5 weeks at the PI's lab. After delivery, we will meet the participant at her home in 1 week, 2 weeks, and 1 month; and then monthly at the PI's lab until 6 months postpartum. Participants will receive \$15/visit compensation. Our team has rich experience in running behavioral interventions for the target population, for instance, most participants (73.9%) in the PI's smoking cessation study have completed 35 one-hour prenatal intervention visits and 12 monthly 1.5-hour postpartum follow-up visits with similar compensation (\$15/hour). The breastfeeding intervention components will include prenatal breastfeeding education, postnatal lactation counseling, family/peer/employer support, contingent financial incentives, and early limited formula milk via syringe (optional for at-risk infants).

**Component #1 - Prenatal breastfeeding education:** To maximize the effect, breastfeeding education will start in late pregnancy (28+ weeks) when the mother and family seriously plan on infant feeding. The breastfeeding plan will cover breastfeeding on demand, pain management, skin-to-skin contact, breastfeeding tips after cesarean section, lactation support, breastfeeding away from home, breast pump, maternity leave, and back-to-work scheduling. Educational approaches will include readings with quizzes (\$2 reward if passed), discussion, video, demonstration and practice with a baby simulator. Prenatal breastfeeding education will be delivered in a group with 6 pairs of participants and their family supporters per group. Physical examination of breasts and nipples will be conducted by a certified lactation counselor (CLC) to address potential issues including infectious conditions, dermatitis, breast masses, breast surgery, and flat or inverted nipples.

**Component# 2 - Postnatal lactation counseling:** A part-time CLC will be hired to provide timely and individualized postnatal lactation counseling. She will monitor each participant's breastfeeding progress, help them initiate breastfeeding immediately after delivery, correct myths and flaws, answer questions, and offer suggestions and tips to solve potential problems. Besides face-to-face meetings, text messages and phone calls will also be used to provide timely assistance of lactation practice and routine checking of feeding status.

**Component #3 - Family/Peer/Employer support:** The participant will nominate a family supporter for her breastfeeding. The family supporter will receive our training for skills in supporting the participant's decision and effort to breastfeed. Other family members will also receive a breastfeeding support booklet. The PI has successful experience of training 16 family supporters for our Pregnancy and Smoking Cessation Study. In addition, we will encourage participants to attend Buffalo's Baby Cafés (6 sites), a breastfeeding drop-in support group, to seek further support from lactation counselors and other breastfeeding mothers (peers). Particularly, the PI has been collaborating with one of these sites, the Durham's Central City Baby Café (see **Letter of Support**). This Baby Café has been helping 214 of 221 mothers (96.8%) to breastfeed successfully since 2013. A booklet on benefits of breastfeeding for business, how to support a nursing mother in workplace, laws and policies of promoting breastfeeding will be available to the participant's employer.

**Component #4 - Contingent financial incentives:** Participants will receive incentives for breastfeeding if they are able to nurse or to provide milk by pumping in the presence of a female research staff. In the Co-I [name] effective intervention (e.g., 72% breastfeeding rate at 6 months postpartum vs. 0% usual care), contingent incentives start at \$20 at the end of first month and increase by \$10 every month until the end of 6 months postpartum. We will adapt this incentive schedule for the proposed project by adding two home visits in week 1 and week 2 postpartum for breastfeeding consultation with \$20 incentive for breastfeeding, given that the first month postpartum is critical to address high risk of breastfeeding discontinuation and smoking relapse. The family supporter will also receive \$10 incentive/month if the participant is still breastfeeding.

**Component #5 - Early limited formula milk (ELF) via syringe:** This component is optional and is only reserved for at-risk infants with 5% or more birth weight loss within the first 2 days of life when the mother decides to add formula. The goal of ELF is to ensure supplemental use of formula to help the at-risk infant grow but will not interrupt the success of breastfeeding. Specifically, the mother should always breastfeed the infant first. If needed, a limited amount (10.0 mL or less) of formula milk is then complemented. The formula milk is administered via syringe rather than baby bottles, which can prevent nipple confusion. ELF will be discontinued once breast milk can meet the infant's need, usually within 2 weeks. ELF has been shown to increase exclusive breastfeeding rate (79% vs. 42% usual care) at 3 months postpartum for at-risk infants.

**b) Control Group.** Participants in the control group will receive a brief pamphlet on the benefits and skills of breastfeeding. They will complete the same frequency of study visits as the intervention group to monitor their feeding plan/practice with a fixed compensation (\$15/visit), regardless of feeding practice.

**c) Fidelity and quality control.** Step-by-step instructions will be used for each visit. The PI will train all research staff. Evaluation will be conducted via exams and trial runs before their interacting with participants. All visits will be audio-recorded for quality assurance and 20% of audio files will be reviewed by the PI.

**Comments.** We decided not to include any education or intervention directly targeting on smoking relapse. This will allow us to test the independent effect of breastfeeding promotion on smoking relapse.

**3.1.7 Follow-up.** To evaluate sustainability of the effects of breastfeeding promotion on smoking relapse, we will follow participants and infants in 9 months postpartum (i.e., 3 months after breastfeeding intervention ends).

**3.1.8 Outcome measures.** The key outcome measures include timing of postpartum smoking relapse (primary) and breastfeeding duration (secondary) derived from data repeatedly collected throughout the study (**Table 1**). Outcomes will be assessed by graduate research assistants who are blinded to group assignments.

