**Timing of maternal postpartum smoking relapse.** The participant will use a calendar to record the daily number of cigarettes smoked, if any, throughout the study period. Based on SRNT guidelines, the date of postpartum relapse will be defined as the first day after delivery on which an ex-smoker has smoked for 7 consecutive days, or has smoked at least once each week over 2 consecutive weeks. Similar definitions were used in previous studies on postpartum smoking relapse. The self-reported smoking abstinence will be biochemically confirmed by urine cotinine tests with HPLC-MS/MS assay performed by an outside laboratory (Kaleida Health Lab, Buffalo, NY). As recommended by SRNT, a cut-off point of 50 ng/mL urine cotinine will be used to define current smoking. There is a possibility that some participants may relapse during pregnancy (*prenatal* smoking relapse). If the relapse happens before randomization, they will be removed from this study. Otherwise, they will continue to receive breastfeeding intervention and be included in intent-to-treat analysis.

**Breastfeeding duration.** We will measure the initiation, duration, and exclusivity of breastfeeding by interviewing the mother at each postpartum visit using a questionnaire modified from 2 US national birth cohorts. Postpartum mothers will report their current feeding method, frequency, and duration of breastfeeding and/or formula use. Breastfeeding status will be visually verified by a female research staff,

looking for one of the following indicators of successful breastfeeding in the infant – audible swallowing, a regular suck/swallow/breath pattern, or visible milk in the infant's mouth after they are not latched anymore. For a mother who pumps milk, staff will observe pumping combined with the resulting milk being fed to the infant. This visual verification of breastfeeding/pumping was acceptable to participants in [name] study.

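### Fixed blocks of 2, with no concealment procedure stated, make half the allocations certain to anyone who knows the block size and history; undisclosed mixed blocks and a fixed randomisation order are a cheap improvement

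*Combined protocol and SAP*

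**What the plan says.** Section 3.1.5 gives the whole method in one sentence: at 28 weeks of pregnancy, eligible women go to intervention (30) or control (30) "using a sequence of random numbers in blocks of 2, which can ensure equal or close numbers of participants between the two groups". The text provided does not say who generates or holds the sequence, or when an assignment is released.

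The surrounding sections matter for opportunity:

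- **Entry.** Under section 3.1.3, women "must be at 28 weeks of pregnancy or earlier to ensure adequate time for prenatal breastfeeding intervention". Consent, a survey and a urine cotinine check come first, and the pre-test visit (section 3.1.4) follows. A woman may therefore be screened well before 28 weeks or close to it.
- **Judgement at entry.** Section 3.1.3 excludes women firmly opposed to breastfeeding (4.8% in the pilot survey) but keeps those with no current intention (28.6%).
- **Removal before allocation.** On prenatal smoking, section 3.1.8 says: "If the relapse happens before randomization, they will be removed from this study".
- **Visibility of the arms.** Section 3.1.6 gives the intervention arm group classes, lactation counselling and cash incentives. By contrast, "Participants in the control group will receive a brief pamphlet on the benefits and skills of breastfeeding".
- **Blinding.** Section 3.1.8 states: "Outcomes will be assessed by graduate research assistants who are blinded to group assignments". Section 3.1.9 adds blinded coders for the mother-infant videos.

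**The concern.** With a block size of 2, the first woman in each pair fixes the arm of the second. In an open trial the first assignment soon becomes apparent to staff who see the visits. Someone who also knows the block size, and has any say over who is randomised next, could place women according to prognosis. Breastfeeding intention is the obvious trait to act on.

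Assessor blinding does not help, because it operates after allocation and the risk arises before it. Section 2 presents randomisation as the way this trial overcomes the self-selection and confounding of observational work, so the allocation step deserves protection. Table 1 records breastfeeding intention at enrolment, so an imbalance would be visible, but intention is not among the covariates listed in section 3.1.10.

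**Working it through.** **Inputs.** From section 3.1.5: block size 2, ratio 1:1, 60 women. From section 3.1.2: 72 as the recruitment figure allowing for attrition. The observer is assumed to know the block size (or the set of possible sizes) and all earlier assignments.

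**The plan's own figure.** 60/2 = 30 blocks with one woman per arm in each, giving 30 and 30. This agrees with section 3.1.5.

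**Predictability with blocks of 2.**

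- Certain: the second slot of each of 30 blocks, so 30/60 = 50%. With 72 women, 36/72 = 50%.
- Guessable: 30 certain + 30 × 0.5 = 45 of 60 = 75%.

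**Alternatives at 60 women.** Fixed sizes are by enumeration. The mixed design is by simulation, with sizes drawn with equal chance and the observer knowing the possible sizes but not the current one.

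| Design | Certain | Correct guesses | Largest running imbalance |
|---|---|---|---|
| Fixed 2 | 30 (50%) | 45.0 (75%) | 1 |
| Fixed 4 | 20 (33%) | 42.5 (71%) | 2 |
| Fixed 6 | 15 (25%) | 41.0 (68%) | 3 |
| Mixed 4 and 6 | 3.3 (about 6%) | 41.4 (69%) | 3 |

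If the size of each mixed block became known, certain slots would rise to about 17, so non-disclosure is part of the benefit.

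**Price of mixed blocks.** With sizes 4 and 6 equally likely, the mean block is 5. A new block therefore starts at any given even-numbered boundary with probability close to 2/5 = 0.4. The list at 60 women then ends:

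- 2 into a block of 4, with probability 0.4 × 0.5 = 0.2; both in the same arm with probability 1/3.
- 2 into a block of 6, with probability 0.2; both in the same arm with probability 2/5.
- 4 into a block of 6, with probability 0.2; split 3 to 1 with probability 2/5.
- On a block boundary otherwise, and so balanced.

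The chance of 31 v 29 is 0.2 × (1/3 + 2/5 + 2/5) = 0.227, about 23%. Nothing worse can occur at 60 women. Relative efficiency is 4 × 31 × 29/60² = 3596/3600 = 0.999.

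**Why the bias cannot be sized.** The order can be steered at a certain slot only if at least two women are waiting. That depends on how women are batched, which the documents do not say. Suppose 60 women reach 28 weeks evenly at random over 52 weeks (the one year of section 3.1.2) or 61 weeks (the 14 months of recruitment in section 3.3). The steerable certain slots, out of 30, are then:

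- randomised on the day: about 2;
- pooled by calendar week: about 11 to 12;
- pooled by fortnight: about 16 to 18.

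Suppose further that staff steered on breastfeeding intention (28.6% without) at every chance. Over 60 or 72 women, the arms would differ in that share by under 2 points, about 8 to 11 points, and about 14 to 18 points respectively. The answer moves roughly tenfold with an assumption that has no basis in the documents. Turning it into a relapse difference would need a further unsupported figure, the gap in relapse risk by intention. These are illustrations; none is a bound.

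**The case against.** The strongest reply is that the opportunity is narrow. Randomisation is tied to gestational age, and consent, cotinine testing and the pre-test visit are already done. For a woman screened early, the slot she will fill is not yet known, so the eligibility judgement matters only near 28 weeks, and the group concerned is small (4.8%). No section says who enrols, who knows the block size or who sets the order. The fidelity check, in which "20% of audio files will be reviewed by the PI", follows randomisation and shows nothing about enrolment. All of this stands, and it is why the point is minor.

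The plan also has a reason for blocks of 2: near-equal arms throughout. That is a fair aim, but mixed blocks meet it almost as well.

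A third objection concerns the remedy. Guessability comes from seeing earlier assignments, which a separate list holder does not hide, and a strict date order would close the main route even with blocks of 2. This also stands. The order rule must therefore accompany the change of block size; mixed blocks then mainly protect the eligibility route and any lapse in the order.

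Two stronger readings are tempting. A reader might infer that the trial has no concealment; the documents are only silent on it, and practice may be better than the text. A reader might also infer that the result is materially threatened, or take one of the steering figures as a ceiling. Neither follows. Batching, motive and knowledge are not documented, and the 28.6% may include women who are excluded: the pilot figures fit 6/21 and 1/21, and if the second is nested in the first, the share among eligible women is 5/20 = 25%. For scale, at 45% v 25% relapse with 30 per arm, the standard error of the difference is √[(0.45 × 0.55 + 0.25 × 0.75)/30] = 0.120, about 12 points.

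**Conclusion.** The point holds as a minor weakness in a stated method. That half the allocations are certain and 75% are guessable is exact, given knowledge of the block size and history. That enrolling staff have this knowledge is plausible in an open trial but is an inference. Any resulting bias is probably small, given the steps that precede randomisation, and its size cannot be derived from the documents. The reason to act is that the improvement costs almost nothing.

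**What to change.** 1. In section 3.1.5, replace blocks of 2 with computer-generated permuted blocks of randomly varying size, for example 4 and 6. Keep the sizes in a restricted document that enrolling staff do not see.
2. Because many slots remain guessable from history, state that women are randomised strictly in order of the date they reach 28 weeks. Release each assignment only after eligibility and the pre-randomisation smoking check are recorded as final. The list should sit with an existing team member not involved in enrolment, or in an automated system. If such a procedure already exists, stating it is enough for this part.

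The cost is a regenerated list, a named holder and two or three sentences. The statistical price is a running imbalance of up to 3 instead of 1, and at worst 31 v 29 at 60 women (about 23% of lists, 99.9% efficiency), which still satisfies the plan's aim of near-equal arms.

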*Maternal negative affect.* Maternal negative affect will be measured at enrollment and all postpartum visits using the Positive and Negative Affect Schedule (PANAS). The 10 items on negative affect include being distressed, upset, guilty, ashamed, hostile, irritable, nervous, jittery, scared, and afraid. Participants will rate their experience of each particular emotion in the past few weeks. With this time frame, its Cronbach's alpha was 0.87 and test-retest reliability was 0.48. In addition, we will measure maternal anxiety with the State-Trait Anxiety Inventory and postpartum depression with the Edinburgh Postnatal Depression Scale.

**3.1.10 Covariates.** We consider partner smoking, maternal secondhand smoke exposure, education, household income, health motivation, perceived social support, as covariates. They may confound our results and will be controlled in data analysis if not comparable between intervention and control groups.

**3.1.11 Economic costs.** We will collect information on intervention (not research and development) costs such as personnel, recruitment, materials, compensation, incentives, and transportation. We will include outcome costs for formula, medical care of NICU stay and sick child visits, and parental absenteeism for infant illness.

**3.1.12 Statistical Analysis.** *Specific Aim 1 (Breastfeeding promotion and postpartum smoking relapse).* The timing of postpartum smoking relapse (outcome) will be analyzed with Cox regression model by including group assignment (intervention vs control), smoking status (1=smoking, 0=non-smoking), the observed time, and significant covariates. The proportional hazard ratio of postpartum smoking relapse between two groups will be calculated. We will estimate Kaplan-Meier survival curves to visually compare smoking trajectories. Intent-to-treat analysis will be used with all randomized participants being included in their originally assigned groups. Dropouts, losses to follow-up, fetal deaths, and miscarriages will be coded as missing data on smoking status. If missing data on smoking status is more than 20%, we will run pattern mixture models and sensitivity analyses. A supplemental analysis will be run to examine *prenatal* smoking relapse during pregnancy.

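### Only intervention women are described as taught in groups; if their outcomes correlate within groups, the planned Cox model understates the standard error

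*Combined protocol and SAP*

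**What the plan says.** Section 3.1.5 allocates individual women, with a block size of two: "eligible participants will be randomized into either the intervention group (N=30) or the control group (N=30) using a sequence of random numbers in blocks of" (the size follows).

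Section 3.1.6 describes how the intervention is delivered: "Participant will complete 13 one-hour intervention visits: 5 during pregnancy and 8 in postpartum". The prenatal visits are weekly, and under Component #1 "Prenatal breastfeeding education will be delivered in a group with 6 pairs of participants and their family supporters per group". After delivery the format changes. Component #2 says "A part-time CLC will be hired to provide timely and individualized postnatal lactation counseling".

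For the comparison arm, section 3.1.6(b) says "Participants in the control group will receive a brief pamphlet on the benefits and skills of breastfeeding" and "They will complete the same frequency of study visits as the intervention group to monitor their feeding plan/practice with a fixed compensation". It describes no group session, and it does not say whether control visits are held one to one.

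Section 3.1.12 has relapse timing "analyzed with Cox regression model by including group assignment (intervention vs control), smoking status (1=smoking, 0=non-smoking), the observed time, and significant covariates". It mentions no cluster, frailty or robust-variance term. Section 3.1.13 contains no design effect, and no ICC appears anywhere in the document.

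**The concern.** This has the shape of a partially nested design: individual randomization, with grouped delivery in one arm only. Women who sit through the same five sessions share the educator's handling of the material, the discussion, each other and each other's supporters. The plan regards peer contact as useful in its own right, since Component #3 sends participants to a drop-in support group. Some resemblance between members of a group, in breastfeeding and perhaps in relapse, is therefore plausible.

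If it exists, 30 intervention women carry less information than 30 independent women. An ordinary Cox model does not know this, so its interval for the hazard ratio is too narrow. The same applies to breastfeeding duration, which is closer to what the sessions teach. Section 3.1.13 says the pilot can test efficacy, and section 3.4 says its data will support a larger grant, so an overprecise estimate would carry forward.

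**Working it through.** **Inputs from the document.** 30 women per arm (3.1.5); 6 women per education group, hence 30/6 = 5 groups (3.1.6); relapse of 45% against 25% at 6 months and 70% against 39% at 9 months, α = 0.05, power 0.80 (3.1.13); 20% attrition (3.2). **Assumed:** the ICC, shown as a range, and a two-sided test.

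**Step 1: the plan's own figures.** Per arm, n = [1.96·√(2p̄(1−p̄)) + 0.842·√(p₁(1−p₁)+p₂(1−p₂))]² / (p₁−p₂)², followed by the continuity correction n' = (n/4)·[1+√(1+4/(n·|p₁−p₂|))]².

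- 6 months: n = 88.1 (89 rounded up); n' = 97.8, so 98.
- 9 months: n = 39.3 (40 rounded up); n' = 45.5, so 46.

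Both stated sizes, 98 and 46, reproduce as calculations for independent women. The sizing therefore makes no allowance for grouping either.

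**Step 2: effect of clustering in one arm.** The design effect DE = 1 + (m−1)·ICC multiplies the variance contribution of the intervention arm only. With equal arms and equal rates, the ratio of true to reported standard error is √((1+DE)/2), and the actual two-sided error is 2·[1−Φ(1.96/ratio)]. For m = 6:

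| Assumed ICC | DE | SE ratio | Actual error |
|---|---|---|---|
| 0 | 1.00 | 1.000 | 5.0% |
| 0.01 | 1.05 | 1.012 | 5.3% |
| 0.02 | 1.10 | 1.025 | 5.6% |
| 0.05 | 1.25 | 1.061 | 6.5% |
| 0.10 | 1.50 | 1.118 | 8.0% |
| 0.20 | 2.00 | 1.225 | 11.0% |

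**Step 3: smaller groups.** With a mean of 4.8 women (6 less 20% attrition), the error is 6.1% at ICC 0.05 and 7.2% at 0.10. With groups of 3, ICC 0.05 gives DE = 1 + 2×0.05 = 1.10 and an error of 5.6%.

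**Step 4: check by simulation.** Log-rank (Cox score) tests were simulated with 30 against 30 women, five groups of 6 in one arm, zero average effect and 70% relapse by 9 months, 20,000 trials per setting. The error was 5.3%, 5.8%, 6.4%, 7.8% and 10.4% at latent correlations of 0, 0.02, 0.05, 0.10 and 0.20. Adding 20% dropout gave 5.2%, 5.8%, 6.3%, 7.4% and 9.9%. The direction and size agree with Step 2.

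**Step 5: what it means for sizing.** Put DE on the intervention arm in the Step 1 formula, without continuity correction: 2p̄(1−p̄) becomes p̄(1−p̄)(1+DE), and p₂(1−p₂) is multiplied by DE. The 6-month requirement rises from 89 per arm to 99 (ICC 0.05) or 110 (ICC 0.10), and the 9-month one from 40 to 45 or 50.

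**Step 6: which correction works with five groups.** In simulated Cox analyses under no average effect, a plain sandwich variance ran at 7% to 9%, so it does not restore the level. A leave-one-group-out jackknife with a Satterthwaite t reference ran at 4.2%, 4.3% and 3.3% at ICC 0, 0.05 and 0.10 (1,200 trials each, Monte Carlo standard error about √(0.05×0.95/1200) = 0.6 points). It is slightly conservative, and it was not examined at 0.20.

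**The case against.** The best counter-argument is that the ICC for relapse may be close to zero. The sessions teach breastfeeding, and section 3.1.6 deliberately leaves out anything aimed at relapse itself, so a group effect would have to reach smoking mainly through feeding. Only 5 of the 13 visits are group sessions, and they end before delivery, while relapse is followed to 9 months postpartum. Postnatal counselling is individual, and incentives depend on each woman's own feeding. This stands: at ICC 0.01 to 0.02 the error is only 5.3% to 5.6%.

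Groups of 6 may also be hard to fill. If 30 intervention women arrive evenly over 12 months, one enters every 52/30 = 1.7 weeks, and the sixth arrives about 5×1.73 = 8.7 weeks after the first. From 28 weeks to an assumed delivery at 40 weeks there are 12 weeks, of which the sessions take about 5. Smaller or rolling groups are plausible and would weaken the effect. This also stands.

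Three stronger readings are tempting, but the documents do not support them:

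- **That the standard error is too small as a matter of fact.** This depends on a positive ICC. If the intervention changed nothing for any woman, group teaching could not create correlation and the ordinary test would remain valid. Inflated error requires group effects that vary around a zero average.
- **That the trial breaches its declared 5% level.** The 0.05 appears only in the sizing for the larger project; no level is set for the pilot's Cox test.
- **That controls are known to be seen individually.** This is inferred from the absence of any described group.

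None of this removes the gap. A positive ICC narrows the interval wrongly whether or not the intervention works, and the plan has no means of detecting it.

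**Conclusion.** The point holds in conditional form. The plan describes grouped teaching in one arm and analyses every woman as independent. For groups of 6 and an assumed ICC of 0.01 to 0.10, the true standard error of the log hazard ratio is about 1% to 12% larger than the one reported, and a nominal two-sided 5% test runs at about 5.3% to 8.0% when group effects vary around a zero average. At ICC zero there is no bias.

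The result rests on an ICC that the documents do not supply, on roughly five stable groups, and on controls having no grouping of their own. Low power at 30 per arm (about 37% at the 6-month rates and 68% at the 9-month rates, before attrition or clustering) is a separate and larger problem. Priority here is low to moderate.

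**What to change.** Record the education group of each intervention woman. If women may join on a rolling basis, define in advance what counts as a group, because leaving out one group at a time needs fixed membership.

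Add to section 3.1.12 that, for Aim 1 and for breastfeeding duration, an interval allowing for clustering by education group will be reported beside the unclustered one. Each control is her own cluster, and a small-sample correction is used because there are only about five groups. A leave-one-group-out jackknife with a t reference is one suitable choice; a frailty term for the intervention groups, or a sensitivity analysis over a range of ICC values, is another. A plain sandwich variance should not be relied on. State before the data are seen which interval is the main one.

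The cost is one extra variable, a sentence or two of analysis text, and a somewhat wider, slightly conservative interval. Visits, treatment and sample size are unchanged.
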